For the vast majority of women who are induced in Alberta (and worldwide), this is accomplished by intravenous oxytocin. An approach that could reduce uterine hyperstimulation with induction of labor is to discontinue the oxytocin infusion once the active phase of labor is reached. This is consistent with bench research that shows that oxytocin stimulates prostaglandin production in the chorio-decidua, which induces positive feedback loops to continue production(8). Furthermore, this idea has been tested in a number of small single centre clinical trials with encouraging results. The 10 trials to date have been summarized by two meta-analyses(9, 10). The number of randomized subjects was modest $n=1,538$ and the sample sizes ranged from 100-250. Most of trials were not of high quality with either high or unclear risk of bias. Only two of the trials were in populations comparable to Canada: one in Europe and one in the USA(11, 12). All trials that reported CS rates documented a reduction with oxytocin discontinuation; pooled OR 0.64 (0.48–0.87). The USA trial observed a reduction in the rate of CS with oxytocin discontinuation compared to continuing from 19.2% (24/125) to 25.2% (32/127) and the European trial the rates were 15% (15/100) vs 22% (22/100). The baseline rates of CS are comparable to our population and the differences they observed were clinically significant. The meta-analyses also observed reductions in the rates of uterine hyperstimulation with oxytocin discontinuation 0.53 (0.33–0.84). While these results are promising, a definitive large randomized controlled trial (RCT) is required to assess important safety outcomes. We propose an initial small pilot study, which will allow us to refine our protocol and will ensure the success of a large multi-centre cluster RCT. Additionally, we also wish to examine serial urine prostaglandin (PG) metabolite levels in a subset of the study population. Our group has completed a large study of PG metabolites (unpublished data) in over 200 women pre-labor and in labor. We have found that prostaglandin F and E metabolites are increased during induced and

Ethics ID: REB21-0614

Study Title: The REDUCE-I Pilot Trial: REDucing the Utilization of CEsaean sections with Induction

PI: [name]

Version 3 & Version date: October 15, 2021

Page 2 of 8

The REDUCE-I Pilot Trial: REDucing the Utilization of CEsarean sections with Induction

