spontaneous labor. We hypothesize that patients who do not need oxytocin restarted may have higher levels or will not have a drop in their urinary PG metabolites. This data could help with improving compliance in future trials. This will also permit a precision medicine approach whereby in the larger trial, the intervention can be offered to those women most likely to benefit.

AIMS: In this REDucing the Utilization of Cesarean sections with Induction (REDUCE-I) Pilot Trial, we propose to answer the following question: Does discontinuation of oxytocin during the active stage of labor (≥ 6 cm dilation) decrease the rate of cesarean section (CS) in induced primiparous women, at term (≥ 37 weeks), with a cephalic presenting singleton fetus without increasing maternal or neonatal morbidity?

METHODS: The REDUCE-I Pilot Trial is a randomized controlled trial (RCT).

Proposed interventions: We will use the modern definition to define the active stage of labor to be ≥ 6 cm dilation(13). The intervention will be to stop oxytocin infusion when a dilation of ≥ 6 cm has been documented. The intervention will be continued until delivery unless contractions decrease to less than 2 in 10 minutes or if no further cervical dilation is noted 4 hours after discontinuation.

Randomization: A computer-generated random allocation sequence will be created by the study statistician. Randomization will stratified by need for cervical ripening and randomization will be blocked. Randomization will take place prior to the initiation of oxytocin.

Blinding: Once a patient is found to be ≥ 6 cm dilation, the study medication will be initiated. Pharmacy will make up identical vials of oxytocin or saline, which will be numbered according to the random allocation sequence created by the study statistician. Nurses will use the blinded vials for ongoing infusion. Patients and caregivers will be blinded.

Inclusion/exclusion criteria: Primiparous women 18 years old or older, at term (≥ 37 weeks) with a cephalic presenting singleton fetus undergoing induction of labor with oxytocin. Multiple pregnancies and known fetal congenital or chromosomal anomalies will be excluded.

Duration of treatment: The treatment period will continue until delivery. If the frequency of the patient's contractions are reduced to less than 2 in 10 minutes or there has been no change in dilation for 4 hours then oxytocin can be restarted.

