In the event a physician or midwife makes a decision to stop the study medication, they have the option to become unblinded by making a request to pharmacy to make it easier for them to know at what dose to continue or re-start oxytocin.

Duration of follow up: Maternal and neonatal follow up until discharge. Postpartum readmission and outcomes will be obtained up to 4 weeks postpartum.

Ethics ID: REB21-0614

Study Title: The REDUCE-I Pilot Trial: REDucing the Utilization of CEsarean sections with Induction

PI: [name]

Version 3 & Version date: October 15, 2021

Page 3 of 8

The REDUCE-I Pilot Trial: REDucing the Utilization of CEsaean sections with Induction

Primary outcomes: 1) CS in labor. 2) Uterine hyperstimulation (occurrence of >5 contractions in 10 minutes). 3) Proportion of screened subjects who agree to enroll in the trial.

Secondary outcomes: Adverse neonatal and maternal outcomes including:

Neonatal: a) Perinatal death; b) Neonatal asphyxia: intrapartum stillbirth or neonatal death from asphyxia (Perinatal Society of Australia and New Zealand coding)(14) or NICU admission and at least two of: i. Apgar score of ≤ 5 at 10 minutes; ii. Mechanical ventilation or chest compressions for resuscitation within 10 minutes; iii. Cord pH < 7.00 (venous or arterial), or arterial base excess ≥ 12 at birth; c) moderate or severe asphyxia (Sarnat)(15) or meets criteria for therapeutic cooling; and d) sepsis or suspected sepsis.

Maternal: a) postpartum hemorrhage (PPH); b) blood transfusion; c) postpartum uterine artery/pelvic artery embolization; d) postpartum hysterectomy; and e) postpartum maternal intensive care unit (ICU) admission.

Compliance: Duration of oxytocin discontinuation. Rate of reintroduction of oxytocin infusion.

Urine Prostaglandin metabolites: Urine samples will be collected every 2 hours during labor from a minimum of 13 women in the intervention group and a minimum of 13 women in the control group. Samples will be aliquoted, frozen, and stored at -80°C prior to analysis. The following five assays will be performed: Prostaglandin E2 ELISA kit (Cayman 514010); Prostaglandin E2 metabolite ELISA kit (Cayman 514531); Prostaglandin F 2α ELISA Kit (Cayman 516011), PGF 2α metabolite, 13,14-dihydro-15-keto Prostaglandin F 2α ELISA Kit (Cayman 516671); and creatinine ELISA kit. Assays will be performed according to manufacturer instructions with appropriate dilutions.

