Measurement of Outcomes: The primary and secondary outcomes will be obtained by detailed chart review by an experienced nurse blinded to allocation. To assess neonatal outcomes, such as hypoxic-ischemic encephalopathy (HIE), data will be obtained by linkage to a specialized asphyxia database in Calgary. This database has collected data on all neonates in Calgary diagnosed with HIE since 2010. Loss to follow-up is not applicable for the current trial as data on all hospital-based deliveries are routinely captured in the medical chart.

Sample Size: The proposed sample size is 200. Approximately 1250 primiparous women are induced each year at Foothills Medical Centre; their CS rate is approximately 30%. A sample of 200 subjects has 30% power to detect an absolute difference of 10% in CS rate and 44% power to detect a difference consistent with previous trials. While under-powered for clinical outcomes, this pilot RCT will allow us to determine an effect size in our population (which will be required to perform a sample size calculation for a larger trial) and will allow us to assess the feasibility of moving forward with a larger study.

Ethics ID: REB21-0614

Study Title: The REDUCE-I Pilot Trial: REDucing the Utilization of CEsaean sections with Induction

PI: [name]

Version 3 & Version date: October 15, 2021

Page 4 of 8

The REDUCE-I Pilot Trial: REDucing the Utilization of CEsaean sections with Induction

Recruitment: We would expect approximately 1250 primiparous women to be induced at Foothills Medical Centre (FMC) over the study period, therefore, we are anticipating approximately a 16% recruitment rate.

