Compliance: Compliance to the treatment is a potential problem. Not all previous studies reported compliance but it is noteworthy that in the USA study that oxytocin was continued in 25% of subjects randomized to discontinuation and restarted in a further 25%(12). This may have been due to concerns regarding the potential adverse effects of longer labor. We note that all the previous studies were performed prior to the release of recent guidelines on labor management (13), which advocated for accepting slow progress in labor and allowing longer labors. These recent guidelines were the intervention we tested in the REDUCED trial, a clustered multi-centre trial which is now completed. Our results did not find any evidence of increased maternal or neonatal risks with longer labors. The intervention site for this study (Foothills Medical Centre [FMC]) was a control site but we plan to move toward adoption of the guidelines at FMC over the next 3-6 months (pandemic permitting). We anticipate that our data will alleviate physician concerns regarding longer labors and encourage patience in managing labor.

Location: Two academic centres will be used for the pilot: FMC in Calgary will be the treatment site, and Royal Alexandra Hospital in Edmonton will be used as a contemporaneous non-intervention control site.

Statistical Analysis: The analysis will be conducted independently by the study statistician ([name]). The primary outcome will not be changed during analysis. The trial, with an explicit statement of the primary outcome, will be registered at clinicaltrials.gov. For dichotomous outcomes relative risks will be calculated and Fisher exact test will be used to assess statistical significance. For continuous outcomes mean differences will be assessed with t-tests after appropriate transformations. Sub-group analysis will be performed by need for cervical ripening. The analyses will be conducted after recruitment for the pilot study has been completed. We will conduct a differences-in-differences analysis using contemporaneous control data from the Royal Alexandra Hospital in Edmonton to monitor for temporal trends in outcomes and changes in labor management.

Timeline: This study will be completed in two years (see figure).

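### The unstratified Fisher test planned for CS is valid but conservative; a stratified Mantel-Haenszel analysis with a 95% confidence interval would be a cheap, minor improvement

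*Combined protocol and SAP*

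**What the plan says.** CS heads the list of three primary outcomes ("Primary outcomes: 1) CS in labor"). The Randomization paragraph states: "Randomization will stratified by need for cervical ripening and randomization will be blocked". The Statistical Analysis paragraph then gives one rule for every binary outcome: "For dichotomous outcomes relative risks will be calculated and Fisher exact test will be used to assess statistical significance". Ripening returns only in this sentence: "Sub-group analysis will be performed by need for cervical ripening". No stratified or adjusted overall comparison is named, and no confidence interval, significance level or sidedness is given. The allocation ratio is not stated either.

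The Sample Size paragraph sets 200 women and a CS rate of about 30%. It says "A sample of 200 subjects has 30% power to detect an absolute difference of 10% in CS rate" and claims "44% power to detect a difference consistent with previous trials", without giving that difference as a number. It also gives the purpose: "this pilot RCT will allow us to determine an effect size in our population". The Background summarises the earlier trials: "All trials that reported CS rates documented a reduction with oxytocin discontinuation; pooled OR 0.64".

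**The concern.** Two features of the plan do not serve its purpose as well as they could.

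First, the design balances the arms within ripening strata, but the test pools over them. Differences in CS rate between the strata then cannot contribute to the treatment contrast, yet a pooled test still counts them as noise. Fisher's test is already conservative because its outcomes are discrete, and pooling makes it more so if ripening predicts CS.

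Second, a pilot meant to inform a larger trial's sample size needs the precision of its estimate more than a p-value, and the plan names only the test.

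Bias and error control are not at stake. What is lost is some power, a test that runs at its nominal level, and a pre-stated interval.

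**Working it through.** **Inputs.** From the Sample Size paragraph: 200 women, control CS 30%, a 10-point difference (taken as 30% versus 20%, following the aim of a reduction). Assumed because not stated: 100 per arm, two-sided 0.05, and the share of women ripened and CS rates by ripening, which are varied.

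**1. The plan's own figure.** Enumerating all pairs from Binomial(100, 0.30) and Binomial(100, 0.20) and summing the probability where Fisher's p is 0.05 or less gives 31.3% power. This reproduces the stated 30%. The uncorrected Pearson chi-square gives 37.1%.

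**2. True size.** The same enumeration at 30% versus 30% gives 3.5% for Fisher and 5.1% for Pearson.

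**3. Effect of the strata.** With half the women ripened, the variance that remains within strata is the mean of p(1 − p) over the two strata, against 0.30 × 0.70 = 0.210 in the pooled test:
- 40%/20%: (0.24 + 0.16)/2 = 0.200
- 45%/15%: (0.2475 + 0.1275)/2 = 0.1875

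The pooled test therefore overstates the noise. The Cochran-Mantel-Haenszel (CMH) statistic without continuity correction is

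[Σ(aₖ − mₖn₁ₖ/Nₖ)]² / Σ[n₁ₖn₀ₖmₖ(Nₖ − mₖ) / (Nₖ²(Nₖ − 1))],

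where, in stratum k, aₖ is CS events in the treated arm, mₖ all CS events, n₁ₖ and n₀ₖ the arm sizes and Nₖ their sum. Arms are equal within strata, and the common odds ratio is chosen so that the overall rates stay at 30% versus 20% (0.583, 0.580, 0.570 and 0.552 by row). CMH figures are simulated, with error of about 0.1 point.

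| Control CS, ripened/not | Size: Fisher | Size: CMH | Power: Fisher | Power: Pearson | Power: CMH |
|---|---|---|---|---|---|
| 30/30 | 3.5% | 5.0% | 31.3% | 37.1% | 37.0% |
| 35/25 | 3.4% | 5.0% | 31.1% | 37.0% | 37.4% |
| 40/20 | 3.1% | 5.0% | 30.9% | 36.8% | 38.6% |
| 45/15 | 2.5% | 5.0% | 30.4% | 36.4% | 40.4% |

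Leaving Fisher's test is worth about 6 points in every row. Stratifying adds nothing, about half a point, just under 2 points and 4 points. With 30% or 70% of women ripened it adds 0 to 3.4 points. Under 2:1 allocation with strata at 40/20, Fisher has size 3.6% and power 30.7%; CMH has 4.9% and 36.5%. With a continuity correction, CMH size drops to about 3.3% to 3.6% and power is 31% when the strata do not differ, so almost nothing is gained.

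**4. Estimate and interval.** At the expected counts of 20/100 and 30/100 the relative risk is 0.667 by either method.
- Crude: SE of the log = √(1/20 − 1/100 + 1/30 − 1/100) = √0.0633 = 0.252, so the 95% CI is 0.407 to 1.092.
- Mantel-Haenszel, with Greenland-Robins variance: 0.407 to 1.092, 0.408 to 1.089, 0.411 to 1.081 and 0.416 to 1.068 down the rows of the table.

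As upper-to-lower ratios, 40/20 gives 1.081/0.411 = 2.63 and 45/15 gives 1.068/0.416 = 2.57, against 1.092/0.407 = 2.68 for the crude interval: about 2% and 4% narrower.

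**5. Blocked randomisation.** Block size is not stated. With permuted blocks of 4 or 6, CMH size is 4.9% to 5.0% and power 37.2% to 40.3%. The two relative risks differ by a median of 0.2% or less, and by under 1.5% in 95% of trials.

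**6. The 44% figure.** It would need restating with any change of test, so its basis matters. These figures assume no CS gap by ripening.
- Pooled odds ratio 0.64: odds 0.4286 × 0.64 = 0.2743, so 0.2743/1.2743 = 21.5%. Power is 22.6% (Fisher) or 27.6% (CMH).
- 0.64 read as a relative risk: 0.30 × 0.64 = 19.2%. Power is 36.4% or 42.6%.
- If 44% is itself a Fisher figure, the treated rate must be 18.1%, and CMH gives 50.4%.

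**The case against.** The strongest reply is that nothing is broken. Fisher's test is valid, and the planned test and the stated 30% agree. One exact test for all binary outcomes is defensible when the list includes perinatal death, hysterectomy and embolization. Most of the power gain has nothing to do with strata: an unstratified Pearson test already reaches 37.1%. The larger stratification gains need a wide gap in CS by ripening, for which the documents offer no evidence. The point estimate does not move, and the interval narrows by a few percent at most and still includes 1. Not mentioning an interval is not a plan to omit one. The basis of the 44% is a separate sample-size question.

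All of this stands as a limit on the size of the point. It does not remove the point. About 50 CS events are expected (30 + 20), enough for large-sample tests to hold their level, so exactness costs power without need for this outcome. Sub-group results by ripening do not provide a stratified overall estimate. If ripening turns out not to predict CS, the stratified test loses nothing material against Pearson, and naming it in advance avoids a later choice between tests.

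**Conclusion.** The concern holds as a minor, optional-looking but worthwhile improvement; it is not an error in the plan. For CS, the planned test runs at about 2.5% to 3.5% instead of 5%, and gives up roughly 6 to 10 points of power for a 10-point difference compared with an uncorrected stratified test. About 6 of those points come from Fisher's test itself. The stratification share, 0 to 4 points, depends on CS rates by ripening that the documents do not report.

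The figures rest on 1:1 allocation and two-sided 0.05; the 2:1 check gives a similar picture. Calling Fisher's test valid refers to type I error for CS alone, with all women analysed as randomised. The trial remains under-powered for CS either way, so the stated interval is of more practical use than the gain in power.

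**What to change.** In Statistical Analysis, specify for CS the Mantel-Haenszel relative risk and risk difference with 95% confidence intervals, stratified by need for cervical ripening, and the Cochran-Mantel-Haenszel test without continuity correction. State the significance level and sidedness.

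Keep exact methods for the rare safety outcomes. No hyperstimulation rate is given, so use the stratified test there only if events are frequent enough, for example if the Mantel-Fleiss criterion exceeds 5. With equal arms that criterion is about half the total events, so this means more than about 10 events. Otherwise keep an exact test.

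In Sample Size, restate both power figures on the new test: 30% becomes about 37% with no CS gap by ripening, and 44% must be recomputed with its assumed effect written down.

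The cost is a few sentences of analysis wording and two restated figures. The stratum is already recorded at randomisation, so no new data are needed.

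### For rare safety outcomes, a relative risk and Fisher p-value alone will often give no interpretable estimate; event counts and a risk difference with a confidence interval should be added

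*Combined protocol and SAP*

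**What the plan says.** The Statistical Analysis section states: "For dichotomous outcomes relative risks will be calculated and Fisher exact test will be used to assess statistical significance". No confidence interval, absolute measure, zero-event rule, significance level or sidedness is given. The section's other analysis that touches outcomes, the difference-in-differences comparison with the Edmonton site, is there to track trends over time and in labor practice. It does not estimate the randomised safety effect.

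The rule therefore covers all the secondary outcomes. On the neonatal side these include perinatal death, asphyxia and sepsis. On the maternal side they run from hemorrhage and transfusion to "c) postpartum uterine artery/pelvic artery embolization; d) postpartum hysterectomy; and e) postpartum maternal intensive care unit (ICU) admission". No expected rate is given for any of them.

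Safety is part of the question under AIMS, which asks whether the CS rate falls "without increasing maternal or neonatal morbidity". The SUSTAINABILITY section makes the application for a large trial depend on the pilot suggesting that CS can be reduced safely. The BACKGROUND, however, leaves important safety outcomes to that larger trial, and the Sample Size section concedes that the pilot lacks power for clinical outcomes.

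**The concern.** A relative risk needs events in the reference arm to be finite, and in both arms to be finite and non-zero. With about 100 women per arm and a rare event, one or both cells may well be empty. The prescribed estimate then fails or collapses to zero, and the Fisher p-value is the only other summary the plan requires. That p-value does not say how large an increase the data leave open. A safety table made up of missing or infinite ratios and non-significant p-values is easily read as showing no increase. A pilot that asks about morbidity, and whose next step depends on apparent safety, should show the range of increases that its data cannot exclude.

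**Working it through.** **Inputs**
- Total size: "The proposed sample size is 200" (Sample Size).
- Allocation ratio: not stated. The Randomization section says only "Randomization will stratified by need for cervical ripening and randomization will be blocked". I assume 100 per arm. Only singletons are eligible, so the count is the same for mothers and babies.
- Test: "Fisher exact test will be used to assess statistical significance". I assume two-sided 0.05, as neither level nor sidedness is given.
- Event rates for safety outcomes: none given. I use a range, with the same true rate *r* in both arms and continued oxytocin as the reference.

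**Step 1. The plan's own figure.** The Sample Size section says "A sample of 200 subjects has 30% power to detect an absolute difference of 10% in CS rate", from a baseline of about 30%. For 30% v 20%, 100 per arm and two-sided 0.05, exact Fisher power is 31.3% (continuity-corrected normal approximation 31.1%; uncorrected 37.1%). The stated 30% is thus consistent with the assumed arm size and level, though it does not prove them. The plan states no power for any safety outcome.

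**Step 2. How often the relative risk fails.** Let *P* = (1 - *r*)^100, the chance of no events in one arm. The relative risk is infinite or undefined when the reference arm is empty (probability *P*). It is undefined when both arms are empty (*P*²). It is zero, infinite or undefined when at least one arm is empty (1 - (1 - *P*)²).

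| Assumed rate | Reference arm empty | Both empty | At least one empty |
|---|---|---|---|
| 0.1% | 0.905 | 0.819 | 0.991 |
| 0.5% | 0.606 | 0.367 | 0.845 |
| 1% | 0.366 | 0.134 | 0.598 |
| 2% | 0.133 | 0.018 | 0.248 |
| 3% | 0.048 | 0.002 | 0.093 |
| 5% | 0.006 | 0.000 | 0.012 |

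Example at 1%: 0.99^100 = 0.366, and 1 - (0.634)² = 0.598. At 3% the relative risk is finite and non-zero with probability 1 - 0.093 = 0.907, about 91%.

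**Step 3. What the Fisher test reports.** With *k* events, all in one arm, and 100 per arm, the two-sided p is 2 × C(100,*k*)/C(200,*k*). For *k* = 3 this is 2 × 161,700/1,313,400 = 0.246. The values for 4, 5 and 6 v 0 are 0.121, 0.059 and 0.029. For 0 v 0, p = 1.

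**Step 4. What a risk difference reports.** The Newcombe interval combines the Wilson limits of each arm. For 0/100 the Wilson upper limit is z²/(n + z²) = 3.84/103.84 = 3.7%. For 3/100 the Wilson limits are 1.0% and 8.5%. For 3 v 0 the lower limit is 3 - √((3 - 1.03)² + 3.70²) = -1.2 points, and the upper limit is 8.5 points.

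| Events per 100 | Relative risk | Fisher p | Risk difference, points (95% CI) |
|---|---|---|---|
| 0 v 0 | undefined | 1 | 0 (-3.7 to 3.7) |
| 1 v 0 | infinite | 1 | 1 (-2.8 to 5.5) |
| 3 v 0 | infinite | 0.25 | 3 (-1.2 to 8.5) |
| 5 v 0 | infinite | 0.059 | 5 (0.3 to 11.2) |
| 6 v 0 | infinite | 0.029 | 6 (1.1 to 12.5) |

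Every table gets an estimate and a bound, including those with no events.

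**The case against.** The strongest reply is that poor detection of harm comes from a sample of 200, which the protocol discloses, and that the safety question is left to a later trial. That stands. Fisher power to detect a doubling is 0.6% from a 1% rate, 4% from 2%, 19% from 5% and 44% from 10%, and no choice of summary repairs it. It does not answer the reporting problem, though: when power is absent, an interval says more than a significance test.

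Four stronger readings are tempting, and the documents do not support them.
- *That the safety question as a whole gets no usable estimate.* The outcomes also include hemorrhage, transfusion and suspected sepsis. If any of these occur at 3% or more, the relative risk is usually finite and non-zero. No rates are given, so which outcomes are affected is itself an assumption.
- *That every table with an empty arm loses its estimate, with p near 1.* Events only in the reference arm give a relative risk of 0, which is defined, although its usual log-scale interval fails. One-empty-arm tables also give p-values as low as 0.059 and 0.029.
- *That the Fisher test can never flag harm below 6 v 0.* This needs exactly 100 per arm and two-sided 0.05, neither of which is stated. One-sided, 5 v 0 gives p=0.030. With a 99/101 split and the events in the smaller arm, two-sided 5 v 0 gives p=0.028.
- *That the relative risk and Fisher test should be dropped for all secondary outcomes.* Where both arms have events the ratio works, so adding to the rule is enough. Nor do the documents give a safety margin against which an upper limit could be judged as pass or fail.

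It is also fair to say that nothing in the plan forbids reporting counts. It simply does not commit to them.

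**Conclusion.** The point holds for the sparse outcomes. Assuming 100 per arm and equal true rates of 0.1% to 1%, the prescribed relative risk is infinite or undefined with probability about 90% to 37%, and zero, infinite or undefined with probability about 99% to 60%. What remains is typically a non-significant p-value that leaves the possible increase unstated: up to 3.7 points for 0 v 0, and up to 8.5 points for 3 v 0. From about 3% upwards the existing rule gives a finite, non-zero ratio in 91% of trials or more. The rates and the equal split are assumptions. The absence of an interval, an absolute measure and a zero-event rule is a matter of the text. This is a gap in reporting and estimation, separate from the shortage of power that the protocol already admits.

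**What to change.** In the Statistical Analysis section, for the secondary neonatal and maternal outcomes:
- report event counts and denominators per arm, and the risk difference with a Newcombe or other score 95% confidence interval;
- keep the relative risk where both arms have events;
- state that a non-significant Fisher p-value is not evidence of safety.

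The rule for CS and hyperstimulation can stay as it is. It would help to state the significance level and sidedness in the same place, and to say that the interval is descriptive, because it can disagree with the Fisher test (at 5 v 0 it excludes zero while p=0.059).

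The cost is a sentence or two. Design, data collection and sample size do not change, and no power is gained. The small downside is that the safety statement will look less reassuring, since the bounds are too wide to show safety for events near 1%.
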